Cover Page

Official Title: Longitudinal Dynamics of Angiotensin II Type 1 Receptor Antibodies and Their Impact on Kidney Transplantation Outcomes

NCT Number: pending

Document Date: 2024-12-09

Study Protocol

1. Study Objectives

The primary objective of this study was to evaluate the impact of longitudinal changes in AT1R-Ab levels during the first year after transplantation on clinical outcomes in kidney transplant recipients. The initial analysis focused on characterizing the trajectory of AT1R-Ab concentrations over time.

Secondary outcomes included the incidence of de novo donor-specific antibody (DSA) formation and changes in renal function by AT1R-Ab group. Renal function was evaluated using serum creatinine (SCr) and estimated glomerular filtration rate (eGFR) at 2 weeks, 3 months, and 1-year post-transplant.

2. Study Design

Design: Retrospective cohort study.

Study Population: Kidney transplant recipients between 2016 and 2022 at Seoul National University Hospital

3. Inclusion Criteria:

Eligible patients were those who had serum samples collected at pre-transplant and at 2 weeks, 3 months, and 1-year post-transplant, with a minimum follow-up of 1 year

4. Exclusion Criteria:

Exclusion criteria were simultaneous multi-organ transplantation and age younger than 18 years.

Statistical Analysis Plan

Group comparisons were performed at four time points: pre-transplant, and at 2 weeks, 3 months, and 1-year post-transplant. Continuous variables were summarized as means with standard deviations and compared using one-way analysis of variance (ANOVA) or Kruskal–Wallis tests, as appropriate. Categorical variables were expressed as frequencies and percentages, and differences between groups were assessed using chi-square tests or Fisher's exact tests.

To visualize longitudinal changes in AT1R-Ab group classification, Sankey diagrams were constructed to illustrate dynamic transitions between antibody groups over time.

The associations between AT1R-Ab groups and post-transplant outcomes, including biopsy-proven acute rejection (BPAR) and de novo donor-specific antibody (DSA) development, were analyzed over follow-up periods of 1 and 3 years using Marginal Structural Cox Models (Cox-MSM). This approach accounted for time-varying confounding and exposure misclassification, and all available time-varying variables were incorporated into the model.

Stabilized inverse probability weights were estimated based on the probability of remaining in a given antibody group at each time point. Covariates included age, sex, body mass index (BMI), pre- and postoperative angiotensin receptor blocker (ARB) use, pre- and postoperative hypertension, donor type, preemptive transplantation, kidney replacement therapy (KRT), donor–recipient relationship, compatibility, and desensitization.

Although the HIGH group became very small by the 1-year time point, the IPW estimates did not diverge. To prevent potential instability due to small cell sizes, stabilized weights were calculated as the product of inverse probability of treatment weighting (IPTW) and inverse probability of censoring weighting (IPCW).

For secondary outcomes, boxplots were generated to visualize the distribution of eGFR and SCr at 2 weeks, 3 months, and 1-year post-transplant by AT1R-Ab group. These graphical analyses illustrated variability, medians, and outliers within each group. Statistical comparisons were performed using parametric or nonparametric tests depending on data distribution. These analyses aimed to evaluate whether higher AT1R-Ab groups were associated with impaired kidney function as reflected by eGFR or SCr levels.

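### The SAP says the Cox-MSM accounted for exposure misclassification, but no step it describes corrects assay or cut-off error in the AT1R-Ab group

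*Combined protocol and SAP*

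**What the plan says.** In the Statistical Analysis Plan, the paragraph on associations between AT1R-Ab group and outcome (biopsy-proven acute rejection, BPAR, and de novo donor-specific antibody, DSA, over 1 and 3 years) credits the Cox-MSM with this property: "This approach accounted for time-varying confounding and exposure misclassification". The claim carries no qualification.

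The next two paragraphs describe how the model was weighted:

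- "Stabilized inverse probability weights were estimated based on the probability of remaining in a given antibody group at each time point", followed by a list of demographic, clinical and transplant covariates.
- "stabilized weights were calculated as the product of inverse probability of treatment weighting (IPTW) and inverse probability of censoring weighting (IPCW", introduced as protection against instability from small cells.

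The exposure is a categorical group derived from samples at four times (pre-transplant, 2 weeks, 3 months, 1 year). The SAP expects patients to move between groups: "Sankey diagrams were constructed to illustrate dynamic transitions between antibody groups over time". It also reports that "the HIGH group became very small by the 1-year time point".

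**The concern.** Inverse probability weights take the recorded group as given. They rebalance measured covariates across recorded groups and adjust for measured predictors of censoring. They contain no information on whether a recorded HIGH is a true HIGH. The SAP nevertheless lists misclassification beside time-varying confounding as something the model dealt with.

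What is at stake is the reading of the BPAR and de novo DSA hazard ratios. A reader who accepts the sentence has no reason to attach a measurement caveat to them. That includes a null result, which non-differential error in a two-group exposure could help to produce.

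**Working it through.** **Step 1. What each described step can address.** The plan gives no misclassification figure to reproduce, so the first check is on the text.

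| Described step | Addresses | Corrects a wrongly assigned group at a visit? |
|---|---|---|
| Group followed across sampling times | Error from a fixed baseline group, within the first year | No |
| Treatment weights (IPTW) on listed covariates | Measured confounding | No |
| Censoring weights (IPCW) | Measured selection by censoring | No |
| Stabilization | Weight variability | No |

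The covariate list has no assay, batch or replicate variable. Neither the Study Protocol nor the SAP gives a cut-off, assay precision, validation data, a misclassification model or a bias analysis.

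**Step 2. Assumed illustration, two groups.** Every input is assumed: true hazard ratio (HR) 2.0, true HIGH share p = 0.10, error unrelated to outcome, a single time point. This is not the full Cox-MSM.

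- Recorded share: m = Se·p + (1 − Sp)(1 − p)
- Truly HIGH among recorded HIGH: PPV = Se·p / m
- Truly HIGH among recorded not HIGH: F = (1 − Se)·p / (1 − m)
- Recorded HR = [1 + PPV(HR − 1)] / [1 + F(HR − 1)]

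| Se / Sp | m | PPV | F | Recorded HR |
|---|---|---|---|---|
| 0.95 / 0.99 | 0.104 | 0.913 | 0.0056 | 1.90 |
| 0.90 / 0.98 | 0.108 | 0.833 | 0.0112 | 1.81 |
| 0.80 / 0.95 | 0.125 | 0.640 | 0.0229 | 1.60 |

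For the last row: m = 0.08 + 0.045 = 0.125; PPV = 0.08/0.125 = 0.640; F = 0.02/0.875 = 0.0229; HR = 1.640/1.0229 = 1.60.

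**Step 3. Does correct weighting restore it?** Assume one measured confounder L, present in 40%. P(HIGH) is 0.18 with L and 0.05 without. The event rate is 0.02 per year, multiplied by 1.8 with L and by 2.0 if HIGH.

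- *True group, weighted.* The average rate over L is 0.4·0.036 + 0.6·0.020 = 0.0264, doubled in HIGH. The ratio is 2.00 (crude 2.42), so weighting removes the confounding.
- *Recorded group at 0.80/0.95, weighted.* With L: m = 0.144 + 0.041 = 0.185, PPV = 0.144/0.185 = 0.778, F = 0.036/0.815 = 0.0442. Without L: m = 0.04 + 0.0475 = 0.0875, PPV = 0.04/0.0875 = 0.457, F = 0.01/0.9125 = 0.0110.
  - Recorded HIGH rate: 0.0144·1.778 + 0.012·1.457 = 0.0431.
  - Recorded not-HIGH rate: 0.0144·1.0442 + 0.012·1.0110 = 0.0272.
  - The ratio of starting rates is 1.59. Over one year of person-time it is 1.58 (crude 1.85).

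The weights remove the confounding by L and leave the misclassification error.

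**Step 4. Is the direction assured?** Assume three groups with true shares 0.70/0.20/0.10 and true HRs 1/1/2. A fraction e of LOW is recorded as MID, e/2 of MID as LOW and e/2 as HIGH, and e of HIGH as MID.

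- e = 0.10: recorded MID = (0.07 + 0.18 + 0.01·2)/0.26 = 1.04; recorded HIGH = (0.01 + 0.09·2)/0.10 = 1.90.
- e = 0.20: recorded MID = (0.14 + 0.16 + 0.02·2)/0.32 = 1.06; recorded HIGH = (0.02 + 0.08·2)/0.10 = 1.80.

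A null middle group moves away from 1, so a general statement that the bias is toward the null would not be safe.

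**The case against.** The strongest defence is contextual. The sentence describes a longitudinal model and follows directly on the paragraph about movement between groups. Exposure misclassification may therefore mean only the error of labelling a patient by the baseline group. Following the group over time does reduce that error. This reading is plausible and part of it stands: that component can be claimed as reduced. But the SAP does not say that this is all it means, and the unqualified wording also covers assay and cut-off error.

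A reader might also infer three stronger things that the documents do not support.

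- *That unobserved group changes between samples, or after the 1-year sample in the 3-year analysis, are uncorrected misclassification.* The Study Objectives set out to "evaluate the impact of longitudinal changes in AT1R-Ab levels during the first year after transplantation on clinical outcomes", so exposure is framed as first-year status. Later or between-visit changes would be error only if the target were continuous true status, which is not claimed. The rule linking each sample to a follow-up interval is not written out, but that is a secondary clarification.
- *That the small HIGH group at 1 year implies severe distortion throughout.* With 2% truly HIGH and 0.80/0.95, the recorded HR would be 1.24. But the recorded HIGH share would then be 0.80·0.02 + 0.05·0.98 = 6.5%, over three times the true share, which fits poorly with a very small group. HIGH also shrank to that size, so it was larger at some earlier point.
- *That the hazard ratios are shown to be biased.* No error rate or estimate is given from which to show it.

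**Conclusion.** The sentence is wrong as written: it attributes to the Cox-MSM a correction that the described steps do not make. The defensible claim covers measured time-varying confounding, censoring and a reduction in fixed-baseline error during the first year. Assay and cut-off error in the group at a visit is uncorrected.

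The actual size and direction cannot be computed. The 1.90 to 1.60 range rests wholly on assumed values (two groups, true HR 2.0, 10% truly HIGH, error unrelated to outcome). It shows that modest error can matter and survives weighting. It does not estimate what happened in this cohort.

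This is a minor-to-moderate point. No result is shown to be wrong, but a bias-control statement attached to the main association analysis should be narrowed.

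**What to change.** 1. Delete the reference to exposure misclassification, or replace it with: *and reduced misclassification from using a fixed baseline group during the first year*.
2. Add: *Assay and cut-off misclassification is not corrected; its size and direction are unknown.*
3. Only if the broader claim is kept, report a quantitative bias analysis over a stated range of sensitivity and specificity beside the main BPAR and de novo DSA hazard ratios.

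As an optional clarification in the same edit, state which sample defines the group in each follow-up interval.

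Items 1 and 2 are wording only, with no new data or re-analysis. The price is a slightly less favourable statement about bias control. Item 3 uses existing data but needs assumed or validation-based error rates. It will be imprecise where HIGH is very small, and it cannot be computed where 1 minus the assumed specificity exceeds the recorded HIGH share.

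### Transplant year is not among the listed weight covariates for a 2016–2022 cohort, so the 1-year and 3-year hazard ratios are both open to era confounding

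*Combined protocol and SAP*

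**What the plan says.** Section 2 (Study Design) defines the cohort as "Kidney transplant recipients between 2016 and 2022" at one hospital. Section 3 (Inclusion Criteria) requires serum at four time points, "with a minimum follow-up of 1 year". The Statistical Analysis Plan states that rejection and de novo DSA "were analyzed over follow-up periods of 1 and 3 years", using marginal structural Cox models.

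The weights are stabilized and formed as the product of treatment weights (IPTW) and censoring weights (IPCW). One covariate list is given, directly after the sentence on the probability of staying in an antibody group. It starts "Covariates included age, sex, body mass index (BMI), pre- and postoperative angiotensin receptor blocker (ARB) use" and goes on to hypertension, donor and relationship variables, pre-emptive transplantation, KRT, compatibility and desensitization. It contains no transplant date, year or era, and neither the protocol nor the SAP stratifies or adjusts for calendar time elsewhere.

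The SAP also says that "all available time-varying variables were incorporated into the model". Transplant year is fixed at baseline, so that sentence does not cover it. No data cut-off, censoring rule or separate covariate list for the IPCW is given. The cover page carries "Document Date: 2024-12-09".

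**The concern.** Treatment weighting removes confounding only by the variables in the weight model. Over seven calendar years, both the mix of antibody groups and the risk of rejection or DSA could have drifted. If both did, part of any difference between AT1R-Ab groups would be a difference between early and late transplants, and the listed covariates need not capture it. This applies to the 1-year hazard ratios as much as to the 3-year ones.

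A secondary issue arises at 3 years only. One year of follow-up is guaranteed, so the latest transplants are censored before 3 years for a reason fixed by their transplant date. That censoring is uninformative only if risk does not depend on transplant date given the variables in the model.

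**Working it through.** The documents state no sample size, event count or hazard ratio, so there is no figure to reproduce. The first two steps are arithmetic under stated assumptions. The last two are illustrations.

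**1. Who cannot reach 3 years.** Inputs: an accrual window of 1 January 2016 to 31 December 2022 (2,557 days), uniform accrual (assumed), and a cut-off no later than the document date (assumed, because the analyses are described in the past tense). The earliest cut-off considered is end-2023, which gives a transplant on 31 December 2022 exactly 1 year. Share = days of accrual less than 3 years before cut-off ÷ 2,557.

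**2. Person-time lost.** With L = late days ÷ 365.25, the loss rises linearly from 0 to L years across the late window. Lost share of 0–3 year person-time = (L²/2) ÷ (7 × 3).

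| Cut-off | Late days | Share of recipients | L (years) | Person-time lost |
|---|---|---|---|---|
| 9 Dec 2024 | 387 | 15.1% | 1.06 | 0.56/21 = 2.7% |
| 30 Jun 2024 | 549 | 21.5% | 1.50 | 1.13/21 = 5.4% |
| 31 Dec 2023 | 730 | 28.5% | 2.00 | 2.00/21 = 9.5% |

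The share of recipients reaches zero only with a cut-off of 31 December 2025 or later, after the document date.

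**3. Size of era confounding, two-era illustration.** Let h be the late-era risk relative to the early era, and q1 and q0 the late-era shares in the HIGH and reference groups. The apparent ratio under a true ratio of 1 is (1 + q1(h − 1)) ÷ (1 + q0(h − 1)). All three inputs are assumed: q1 = 0.5, q0 = 0.3, h = 0.5 or 0.7.
- h = 0.5: 0.75/0.85 = 0.88
- h = 0.7: 0.85/0.91 = 0.93
- With the shares reversed: 1.13 and 1.07

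**4. Size of era confounding, simulation.** This used an ordinary Cox model with a fixed binary group, true hazard ratio 1, baseline hazard 0.06 per year, uniform accrual and a cut-off of 9 December 2024. Each figure averages 10 runs of 40,000, with a Monte Carlo standard error of about 0.01.

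| Group odds per year | Hazard per year | HR without year | Same, no early cut-off | HR with year |
|---|---|---|---|---|
| 1.16 | 0.90 | 0.93 | 0.95 | 1.00 |
| 0.86 | 0.90 | 1.08 | 1.06 | 1.00 |
| 1.28 | 0.82 | 0.83 | 0.83 | 1.01 |
| 0.78 | 0.82 | 1.18 | 1.20 | 1.01 |

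When year was related only to group or only to outcome, the estimate without year stayed at 1.00–1.01. Removing the early cut-off changed the estimate by at most about 0.02, close to simulation noise. Almost all of the distortion is therefore confounding rather than censoring.

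**The case against.** The strongest reply is that this could be said of most multi-year retrospective cohorts. Confounding needs year to relate to both group and outcome, and the documents show neither. Donor type, compatibility, desensitization and ARB use may carry part of any era effect. The assumed trends have no source in the documents. The HIGH group is described as very small by 1 year, so its sampling error may well exceed these shifts. All of this stands and limits the point to an unaddressed risk. It does not remove the point: partial proxies cannot be assumed to replace year, and the plan includes no check.

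The list may also be non-exhaustive. If year was used, saying so settles the matter; nothing in the text shows that it was.

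Three stronger readings are tempting, and the documents do not support them:
- *The 3-year results are compromised by dependent censoring.* The share of recipients affected looks large, but the person-time lost is small and the censoring hardly moves the simulated estimate. Reasons for censoring and numbers censored are not reported, so its main driver cannot be stated either.
- *Year was left out of the IPCW.* The one list follows the exposure-model sentence. The covariates of the censoring model are unspecified, which is different from omitting year.
- *The 1-year and 3-year analyses describe different patients.* Every recipient contributes to both, and staggered entry is routine in Cox analysis.

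**Conclusion.** The point holds as an omission from the stated adjustment set, not as a demonstrated bias. Transplant year is absent from the only covariate list for a seven-year cohort, and both time horizons are exposed if year is linked to both AT1R-Ab group and outcome. Under the assumed trends, a true hazard ratio of 1 would appear as roughly 0.83 to 1.18; with only one of the two links there would be essentially no distortion. Truncated follow-up is secondary: 15–29% of recipients but 3–10% of person-time, resting on uniform accrual and on a cut-off between end-2023 and the document date. The change is worth making because it is cheap and would either correct the estimates or show that they are robust.

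**What to change.** - Add transplant year (a linear term, or 2–3 eras) to the IPTW model. If year is also placed in the numerator of the stabilized weights, the weights no longer remove its confounding, so include it in the outcome Cox model as a covariate or stratum.
- Report the weighted balance of transplant year across AT1R-Ab groups.
- State the data cut-off, the censoring rule and the IPCW covariates.
- Treat end-of-data censoring as ordinary administrative censoring. Do not model it with year in the IPCW, because transplant date and cut-off together determine it and positivity fails. With a 9 December 2024 cut-off, recipients transplanted in 2022 remain uncensored at 2.5 years only if transplanted by 9 June (160/365 = 0.44), and none do at 3 years. With year in the denominator only, their stabilized weight would be about 2.1 at 2.5 years ((1 − 205/2,557) ÷ 0.44, where 205 = 365 − 160) and undefined at 3 years.
- Repeat the 3-year model in recipients transplanted at least 3 years before the cut-off.

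The cost is one variable that should already be on record for every recipient, one or two extra parameters in the weight model, and a rerun. Because the HIGH group is already very small, the weight distribution should be checked after year is added.

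### The listed weight-model covariates name neither HLA mismatch nor preformed DSA, so the AT1R-Ab hazard ratios for rejection and de novo DSA may carry residual confounding by immunological risk

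*Combined protocol and SAP*

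**What the plan says.** The Statistical Analysis Plan fits marginal structural Cox models over 1 and 3 years for outcomes "including biopsy-proven acute rejection (BPAR) and de novo donor-specific antibody (DSA) development". Section 1 of the Study Protocol also names "the incidence of de novo donor-specific antibody (DSA) formation" as a secondary outcome.

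The stabilized weights are the product of treatment and censoring weights. Their covariate list opens with "Covariates included age, sex, body mass index (BMI), pre- and postoperative angiotensin receptor blocker (ARB) use" and closes with "compatibility, and desensitization". Between these stand hypertension before and after surgery, donor type, pre-emptive status, kidney replacement therapy and the donor–recipient relationship. Compatibility is not defined. The plan also states that "all available time-varying variables were incorporated into the model".

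Section 3 requires "serum samples collected at pre-transplant and at 2 weeks, 3 months, and 1-year post-transplant" and at least a year of follow-up. Section 4 excludes only multi-organ recipients and those under 18. HLA mismatch, preformed DSA and HLA sensitization are not mentioned anywhere in the documents.

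**The concern.** Rejection and de novo DSA are both alloimmune events. Donor–recipient HLA difference and pre-existing anti-donor antibody are natural candidates for common causes of these outcomes and of AT1R-Ab group. A marginal structural model recovers the exposure effect only if the weights account for the common causes of exposure and outcome. If poorly matched or already sensitized recipients sit more often in the higher AT1R-Ab groups, and the listed covariates do not absorb that difference, the hazard ratio credits AT1R-Ab with risk that belongs to HLA alloimmunity. The study exists to estimate that association, and the plan describes neither a covariate balance check nor a sensitivity analysis for unmeasured confounding. A reader of the results could not tell whether the bias is nil or material.

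**Working it through.** The documents give no sample size, event count, prevalence or effect size, so there is no figure of the plan's own to reproduce. The check is a reading of the covariate list, followed by an illustration on assumed inputs.

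**1. Is either variable in the list?** No item is HLA mismatch or preformed DSA. Three items may carry part of the information:
- Desensitization does not identify recipients with preformed DSA who were not desensitized, and it does not grade mismatch.
- Donor–recipient relationship reflects HLA similarity only loosely.
- Compatibility could mean ABO, HLA or crossmatch compatibility, and the text does not say which.

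**2. Does anything else in the plan cover them?** The catch-all concerns time-varying variables, whereas HLA mismatch and pre-transplant DSA are baseline variables. The exclusions leave recipients with preformed DSA in the cohort.

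**3. Are the data likely to be held?** The Cox outcome "de novo donor-specific antibody (DSA) development" can be classified only if donor HLA type is known (for *donor-specific*) and a pre-transplant antibody result exists (for *de novo*). This is an inference from the outcome's meaning and is not stated in the documents. Section 3 requires serum samples, which is not the same as HLA results. A mismatch count also needs recipient typing. Pre-transplant DSA is therefore the more secure of the two.

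**4. How large could the bias be?** Take one omitted binary factor with prevalence p1 in the higher and p0 in the lower AT1R-Ab group, and risk ratio RR for the outcome. If AT1R-Ab has no effect, the apparent ratio is

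B = (1 + p1(RR − 1)) / (1 + p0(RR − 1)).

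All inputs are assumptions.

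| p1 vs p0 | RR 1.5 | RR 2 | RR 3 |
|---|---|---|---|
| 20% vs 20% | 1.00 | 1.00 | 1.00 |
| 20% vs 10% | 1.05 | 1.09 | 1.17 |
| 30% vs 10% | 1.10 | 1.18 | 1.33 |
| 40% vs 10% | 1.14 | 1.27 | 1.50 |

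Example: 40% vs 10% with RR 3 gives (1 + 0.4 × 2)/(1 + 0.1 × 2) = 1.8/1.2 = 1.50. With a reference prevalence of 20%:
- RR 1.5 and 30% vs 20% gives 1.15/1.10 = 1.05.
- RR 2 and 40% vs 20% gives 1.4/1.2 = 1.17.
- RR 3 and 50% vs 20% gives 2.0/1.4 = 1.43.

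Now let a listed covariate capture a share s of those with the factor, with no false positives. Among those it does not flag, the prevalence falls to q = p(1 − s)/(1 − ps), and q replaces p in the formula. For 30% vs 10%:

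| Share captured | RR 1.5 | RR 2 | RR 3 |
|---|---|---|---|
| 0% | 1.10 | 1.18 | 1.33 |
| 50% | 1.06 | 1.12 | 1.22 |
| 80% | 1.03 | 1.06 | 1.11 |
| 100% | 1.00 | 1.00 | 1.00 |

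Example: s = 0.5 gives q1 = 0.15/0.85 = 0.176 and q0 = 0.05/0.95 = 0.053. At RR 2 this is 1.176/1.053 = 1.12.

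The formula is for a point exposure in two groups and a risk ratio. The planned analysis has a time-varying, multi-group exposure and a hazard ratio, so these values are only a rough guide.

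**5. Where would the covariates have to enter?** A stabilized weight is a ratio of two probabilities. A baseline covariate in both the numerator and the denominator largely cancels, so exposure still depends on it in the weighted sample. It then has to be in the Cox model too. If it is in the denominator only, the weights themselves do the adjustment. The plan does not say which covariates are in the numerator.

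**The case against.** The strongest reply is that omission is not confounding. The omitted factors must differ across AT1R-Ab groups after the listed covariates are taken into account, and the documents report no such association. That stands. A reader might infer that the AT1R-Ab effect *is* confounded by HLA risk, but the text supports only that it may be.

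Secondly, compatibility might itself mean HLA or crossmatch compatibility, and desensitization and donor–recipient relationship add further information. This also stands in part. The proxies could shrink the bias, and full capture would remove it. They are unlikely to capture mismatch count, or preformed DSA in recipients who were not desensitized.

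Thirdly, the list is introduced in a way that may not be exhaustive. If so, one sentence naming the remaining covariates resolves the matter.

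Fourthly, a reader might take the de novo outcome as proof that both variables are on file. The documents do not describe HLA or DSA methods or their completeness, and recipient typing is a separate requirement.

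Finally, the plan itself says that the HIGH group was very small at 1 year. Covariates that predict group strongly would make the weights more variable. That is a genuine cost of the change, though not a reason to leave the question unaddressed.

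**Conclusion.** The point holds as a gap in the stated adjustment set, with possible residual confounding as its consequence. The gap itself is plain from the text: neither variable is listed, the catch-all does not reach baseline variables, and recipients with preformed DSA are eligible. The size of any bias cannot be determined from the documents. For a single binary factor that is more common in the higher AT1R-Ab group, the assumed inputs give a factor from 1.00 to about 1.4–1.5. The lower end needs no prevalence gap or full capture by listed covariates; the upper end needs a 30-point gap, a risk ratio of 3 and no capture. It would be wrong to read any interior value, such as 1.17, as an estimate for this study. The change is a cheap improvement that should be made. The documents do not show that the results are invalid without it.

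**What to change.** - Add pre-transplant DSA (yes/no) and, where recipient typing is held, HLA mismatch count to the denominator models of both the treatment and the censoring weights. If they are also placed in the numerator, include them in the Cox outcome model. If either is left out, say why.
- State which covariates are in the numerator and which in the denominator.
- State whether compatibility means ABO, HLA or crossmatch compatibility, and drop it if the new variables make it redundant.
- Report weighted standardized differences for these variables across AT1R-Ab groups, and the distribution of the weights at each time point.
- Report results with truncated weights alongside the main analysis.

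The cost is up to two baseline covariates and a rerun of the weight and outcome models. If the inference about the de novo outcome is right, pre-transplant DSA is already held; the mismatch count depends on recipient typing. The downside is more variable weights, most of all in the HIGH group at 1 year, which is why the weight distribution and the truncated analysis belong in the report.

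### Change in renal function by AT1R-Ab group is a secondary outcome, but the SAP specifies only unadjusted comparisons of eGFR and SCr levels at each visit

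*Combined protocol and SAP*

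**What the plan says.** Section 1 of the Study Protocol (Study Objectives) names two secondary outcomes: de novo DSA and "changes in renal function by AT1R-Ab group". It continues: "Renal function was evaluated using serum creatinine (SCr) and estimated glomerular filtration rate (eGFR) at 2 weeks, 3 months, and 1-year post-transplant". It defines no reference visit, change score or slope.

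The Statistical Analysis Plan has two rules that could cover these measures. The general rule is that "Group comparisons were performed at four time points: pre-transplant, and at 2 weeks, 3 months, and 1-year post-transplant", with ANOVA or Kruskal–Wallis for continuous variables. The rule for secondary outcomes is boxplots at the three post-transplant visits, followed by "Statistical comparisons were performed using parametric or nonparametric tests depending on data distribution". The stated aim is to learn "whether higher AT1R-Ab groups were associated with impaired kidney function as reflected by eGFR or SCr levels".

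Adjustment appears in one place. Associations of AT1R-Ab group with post-transplant outcomes, of which biopsy-proven rejection and de novo DSA are named, "were analyzed over follow-up periods of 1 and 3 years using Marginal Structural Cox Models (Cox-MSM". The covariate list and the stabilized weights continue the description of that model.

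**The concern.** Two things do not fit together.

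First, the outcome is worded as change and the analysis is of levels. A test at one visit says whether groups differ at that visit. It does not say whether function moved differently between groups from 2 weeks to 1 year.

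Second, this is a non-randomised cohort. The plan treats age, donor type, desensitization and other factors as confounders for rejection and DSA. It then tests renal function in the same patients without them, and gives no reason. Donor and recipient factors may also bear on eGFR and SCr. If they differ between AT1R-Ab groups, an unadjusted difference mixes their effect with that of the antibody group.

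At stake is the interpretation of a named secondary outcome. Readers could take six sets of unadjusted comparisons (2 measures × 3 visits) as evidence about change, or about an independent association with AT1R-Ab, and the stated analysis provides neither.

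**Working it through.** The plan states no figure on this point, so there is none to reproduce. The check is mainly textual.

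**Outcome against analysis**

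| Item | Study Objectives | SAP |
|---|---|---|
| Quantity | change in renal function, by group | levels of eGFR and SCr, by group |
| Times | 2 weeks, 3 months, 1 year | the same, each visit separately |
| Over-time contrast | none defined | none |
| Estimate with interval | none defined | none; boxplots and tests |
| Covariates or weights | not addressed | described for the Cox model only |

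**Can change be recovered from the level results?** Only in part. If the same patients stay in the same groups, subtracting group means gives a point estimate of mean change. Its precision does not follow, because the SD of change is SD × √(2(1 − ρ)) and the within-patient correlation ρ is not reported. Taking SD 18 mL/min as an assumption:

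- ρ = 0.5: 18 × √1.0 = 18.0
- ρ = 0.7: 18 × √0.6 = 13.9
- ρ = 0.8: 18 × √0.4 = 11.4

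The subtraction also fails if patients are regrouped at each visit, because it then mixes change in function with change in membership. Membership does move: "Sankey diagrams were constructed to illustrate dynamic transitions between antibody groups over time". The SAP does not say which visit's group enters the renal tests.

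**Does the Cox adjustment reach renal function?** The list of Cox outcomes is introduced as non-exhaustive. But a Cox model analyses time to an event, no renal event is defined, and continuous eGFR or SCr cannot be its outcome.

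**How large could confounding be?** The documents cannot answer this. The following is assumption-only. For a binary confounder such as donor type, spurious level difference = imbalance between groups × eGFR gap between donor types.

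- No imbalance: 0
- 0.10 × 5 = 0.5 mL/min
- 0.20 × 8 = 1.6 mL/min
- 0.30 × 10 = 3.0 mL/min

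For a two-group t-test with 160 other patients, the standard error is SD × √(1/n + 1/160), where n is the number in HIGH. With SD 18 this is 5.87 for n = 10 and 3.18 for n = 40. A nominal 5% test then rejects in about 6% to 8% of cases at a bias of 1.6. With no imbalance the rate stays at 5.0%. Reaching 20.3% needs every input at its most adverse assumed value: bias 3.0, SD 15 and 40 in HIGH.

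**The case against.** The strongest reply is that the word change is used loosely. Study Objectives moves straight from it to eGFR and SCr at three visits, and the SAP speaks of levels, so level by group across visits may be all that was intended. This is plausible, and it means a reader should not infer that the investigators set out to measure within-patient change and then left it out. It does not close the gap. Even on the loose reading no over-time contrast is specified, and the two sections should agree.

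A second reply is that the SAP asks only about association, makes no causal claim for these analyses and presents them with boxplots. That stands as far as it goes. But the plan adds statistical comparisons and does not label them unadjusted or descriptive.

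Two stronger readings are tempting and should be resisted. One is that the renal comparisons are biased, or that their false-positive rate is as high as a fifth. The documents show no imbalance, group sizes or SDs. The rates above also use a two-group t-test, whereas the general rule is ANOVA or Kruskal–Wallis across an unstated number of groups. The other is that moving group membership invalidates the tests. Same-visit grouping is the natural reading of the general rule, and comparisons within a visit are not affected by reclassification. Only reading across visits is.

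A fair caution also applies to the remedy. The primary objective concerns changing AT1R-Ab levels, the SAP reports that HIGH became very small by 1 year, and 11 pre-transplant covariates are listed. A model with a fixed group and the full list would lose the changing exposure and ask too much of the data.

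**Conclusion.** The point holds as a mismatch between a named secondary outcome and its analysis, together with a lack of adjustment that the plan itself uses elsewhere. As written, the plan yields no estimate or interval for change in renal function by group. Its level comparisons cannot separate AT1R-Ab group from donor or recipient differences. Both conclusions rest on the text alone and need no assumed figure.

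The effect on the results is unknown in size and direction, and could be nil. The outcome is secondary, so this should be corrected, but it does not bear on the rejection and DSA analyses.

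**What to change.** Keep the boxplots and existing tests, and label them unadjusted and descriptive. Then add:

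1. **Model.** One repeated-measures model for eGFR and one for log SCr, with AT1R-Ab group, visit and group-by-visit terms.
2. **Covariates.** A short set from the pre-transplant factors already listed, for example age, sex, donor type and desensitization. Avoid overlapping pairs such as preemptive transplantation with KRT. If numbers allow, add covariate-by-visit terms for donor type and age, so that change as well as level is adjusted.
3. **Group.** State which visit's group is used. If it is fixed at one sample, say that later changes of group are not captured. A weighted model with time-varying group is an optional sensitivity analysis. It could reuse the existing weights where postoperative covariates are dated by visit.
4. **Reporting.** Give adjusted differences at each visit and change from 2 weeks to 1 year, with 95% intervals. Both are needed, because change from 2 weeks leaves out any difference already present by then.
5. **Label.** Mark the addition as post hoc, since the SAP describes completed work.

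The cost is a modest extra analysis of measures and covariates already named. There are two downsides. Eligibility is tied to serum samples ("Eligible patients were those who had serum samples collected at pre-transplant and at 2 weeks, 3 months, and 1-year post-transplant") and not to renal measurements, so some eGFR or SCr values may be missing; report how many. Intervals for HIGH will also be wide. As an unadjusted illustration only, assuming SD 18 and 160 others, the 95% half-width for a level difference is about 6.3 mL/min with 40 in HIGH and 11.6 with 10. For change at ρ = 0.7 it is about 4.9 and 9.0. Precision under the adjusted model may differ.

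If the model is not added, the least that is needed is to reword the outcome as level at each visit, state the group's visit and label the tests unadjusted. That makes the document consistent but supplies neither change nor adjustment.
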